13.0 Treatment/Follow-up Decision at Evaluation of Patient

- 13.1 Patients will be evaluated for response after 2 cycles of treatment. Patients who are NMR or PMD after 2 cycles of treatment will discontinue treatment and go to the event-monitoring phase per Section 18.0. Patients who are CMR or PMR will continue treatment per protocol.
- 13.2 Patients who develop progressive disease by either PET-CT based (PMD) or CT based (PD) response criteria (see Section 11.0) at any time while receiving therapy or during observation will go to the event-monitoring phase per Section 18.0.
- 13.3 Patients who go off protocol treatment for unacceptable adverse events, subsequent treatment or refusal will go to the event-monitoring phase per Section 18.0.
- 13.4 Observation: The patient will be observed every 30 days x90 days then every 90 days x 2.5 years, then every 6 months until 5 years from registration. If the patient develops disease progression (see section 13.2) or receives subsequent treatment before disease progression while in observation, they will go directly to the event monitoring phase per section 18.0.
- 13.5 Patients who achieve a PMR or CMR will receive a maximum total of 8 cycles of treatment. After 8 cycles, they go to observation per Section 13.4 above.
- 13.6 Early Safety Analysis Phase Only: If a patient fails to complete the first cycle (21 days) of treatment for reasons other than toxicity, the patient will be regarded as in evaluable and will be replaced.

- 13.7 A patient is deemed *ineligible* if after registration, it is determined that at the time of registration, the patient did not satisfy each and every eligibility criteria for study entry. The patient may continue treatment off-protocol at the discretion of the physician as long as there are no safety concerns, and the patient was properly registered. The patient will go directly to the event-monitoring phase of the study (or off study, if applicable).
- If the patient received treatment, all data up until the point of confirmation of ineligibility must be submitted. Event monitoring will be required per Section 18.0 of the protocol.
 - If the patient never received treatment, on-study material and the End of Active Treatment/Cancel Notification Form must be submitted. No further data submission is necessary.

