- 16.22 **Sample Size:** The one stage study design with an interim analysis to be used is fully described above. A minimum of 25 and a maximum of 56 evaluable patients will be accrued onto this phase II study at the final dose level determined in the safety analysis phase, unless undue toxicity is encountered. An additional one or two cohorts of 6 patients will be accrued if the early safety analysis determines that a reduction to the starting dose is warranted for up to 12 additional evaluable patients. We anticipate accruing up to an additional 7 patients (2 safety analysis, 5 phase II) to account for ineligibility, cancellation, major treatment violation, or other reasons (i.e. replacement of a safety analysis patient) for a total of 75 patients overall.
- 16.23 **Accrual Rate and Study Duration:** The anticipated accrual rate is 25-30 evaluable patients per year. At this rate, it will likely take about 3 years to enroll all patients. The maximum total study duration is expected to be approximately 3.5 years, or until the last patient accrued has been observed for at least 6 months.
- 16.24 **Power and Significance Level:** Assuming that the number of successes is binomially distributed, the significance level is .10, i.e. there is a 10% chance of finding the drug to be effective when it truly is not. The probability of declaring that this regimen warrants further study (i.e. statistical power) and the probability of stopping at the interim analysis under various success proportions can be tabulated as a function of the true success proportion as shown in the following table.

If the true success proportion is...	0.65	0.70	0.75	0.80
Then the probability of declaring that the regimen warrants further study is...	0.10	0.29	0.59	0.85
And the probability of stopping at the interim analysis is...	0.69	0.49	0.27	0.11

- 16.25 **Other considerations:** Adverse events, quality/duration of response, and patterns of treatment failure observed in this study, as well as scientific discoveries or changes in standard care will be taken into account in any decision to terminate the study

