- 16.322 Duration of response is defined for all evaluable patients who have achieved a response as the date at which the patient's objective status is first noted to be a CMR or PMR to the earliest date progression (PMD or PD) is documented. If a patient has not had disease progression, they will be censored on the date of their last disease assessment. The distribution of duration of response will be estimated using the method of Kaplan-Meier.
- 16.322 Progression-free survival is defined as the time from registration to the earliest date of documentation of disease progression (PMD or PD) or death due to any cause. If a patient is alive and has not had disease progression, they will be censored on the date of their last disease assessment. The distribution of progression-free survival will be estimated using the method of Kaplan-Meier.
- 16.323 Overall survival time is defined as the time from registration to death due to any cause. If a patient is still alive, they will be censored on the date of their last follow-up. The distribution of overall survival will be estimated using the method of Kaplan-Meier.
- 16.324 Adverse Events: All eligible patients that have initiated treatment will be considered evaluable for assessing adverse event rate(s). Adverse events will be assessed using CTCAE version 4.0 per Section 10.0. The maximum grade for each type of adverse event will be recorded for each patient, and frequency tables will be reviewed to determine patterns. Additionally, the relationship of the adverse event(s) to the study treatment will be taken into consideration.
- 16.33 Correlative Outcome Analyses: Due to the small overall sample size, the results of these analyses will be considered exploratory and hypothesis-generating in nature.
- 16.331 Biomarkers including intratumoral cell populations, genetic variability, serum cytokines, and T-cell activation will be evaluated both before and during treatment. Baseline values and changes in these parameters over time will be both graphically

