- 16.51 The principal investigator(s) and the study statistician will review the study at least twice a year to identify accrual, adverse event, and any endpoint problems that might be developing. The Mayo Clinic Cancer Center (MCCC) Data Safety Monitoring Board (DSMB) is responsible for reviewing accrual and safety data for this trial at least twice a year, based on reports provided by the MCCC Statistical Office.
- 16.52 Adverse Event Stopping Rules (to include all patients treated at the dose level determined in the early safety analysis): The stopping rules specified below are based on the knowledge available at study development. We note that the Adverse Event Stopping Rule may be adjusted in the event of either (1) the study re-opening to accrual or (2) at any time during the conduct of the trial and in consideration of newly acquired information regarding the adverse event profile of the treatment(s) under investigation. The study team may choose to suspend accrual because of unexpected adverse event profiles that have not crossed the specified rule below. Accrual will be temporarily suspended to this study if at any time we observe events considered at least possibly related to study treatment (i.e. an adverse event with attribute specified as "possible," "probable," or "definite") that satisfy one of the following:
- if 5 or more patients in the first 15 treated patients experience a grade 4 or higher non-hematologic adverse event at least possibly related to treatment.

- if after the first 15 patients have been treated, 30% of all patients experience a grade 4 or higher non-hematologic adverse event at least possibly related to treatment.

We note that we will review grade 4 and 5 adverse events deemed “unrelated” or “unlikely to be related”, to verify their attribution and to monitor the emergence of a previously unrecognized treatment-related adverse event.

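### Reported adverse event rates leave out treated patients later ruled ineligible, although the toxicity stopping rule counts them

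*Combined protocol and SAP*

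**What the plan says.** - **Section 16.324 (adverse event analysis):** "All eligible patients that have initiated treatment will be considered evaluable for assessing adverse event rate(s"). The maximum grade of each event type is then tabulated per patient. No other safety table covering all treated patients is planned.
- **Section 13.7 (ineligible patients):** ineligibility is decided after registration, if it emerges that at registration "the patient did not satisfy each and every eligibility criteria for study entry". No time limit is given. Patients who have already been dosed are foreseen: "If the patient received treatment, all data up until the point of confirmation of ineligibility must be submitted". Event monitoring under Section 18.0 is also required for them.
- **Section 16.52 (adverse event stopping rules):** the population is "to include all patients treated at the dose level determined in the early safety analysis". Eligibility is not mentioned.
- **Section 16.22 (sample size):** "A minimum of 25 and a maximum of 56 evaluable patients will be accrued onto this phase II study" at the final dose level. On losses: "We anticipate accruing up to an additional 7 patients (2 safety analysis, 5 phase II) to account for ineligibility, cancellation, major treatment violation", among other reasons.
- **Section 2.22:** safety and tolerability of the regimen is a secondary goal.

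**The concern.** The plan has two safety populations that differ by an eligibility filter. A treated patient at the final dose level who has a related grade 4 non-hematologic event counts toward suspending accrual under 16.52. If that patient is later ruled ineligible, the event does not appear in the rates under 16.324, although the data have been submitted.

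Exposure to the drugs determines who is at risk of toxicity, and a later eligibility ruling does not undo exposure. The filter would be harmless if rulings were unrelated to toxicity, but the criteria give some reason for doubt:

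- A history of interstitial lung disease is excluded (3.25). Section 15.27 lists interstitial pulmonary disease at 6% and pneumonitis at up to 6% for nivolumab.
- Known or suspected autoimmune disease is excluded (3.23, 3.25). Section 15.27 lists many immune-mediated events.
- Neuropathy of grade 2 or higher is excluded (3.29d). Section 15.17 lists neuropathy among the toxicities seen in 10% or more of patients on brentuximab vedotin.

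The study has a single arm, so eligibility may be re-examined when the toxicity is already known. Some criteria also leave room for either ruling: 3.23 admits certain autoimmune conditions, while 3.25 excludes a prior history of known or suspected autoimmune disease. If patients with such conditions have more events and are removed more often, the reported rates are too low. Section 7.1 describes the combination as not studied before, so these rates would be among the first evidence on its toxicity.

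**Working it through.** **1. The plan's own count.** Section 16.22 gives 56 evaluable patients, up to 12 in extra dose-level cohorts, and 7 for losses: 56 + 12 + 7 = 75, which matches the stated total. The 7 are the only figure that bears on how many treated patients might be ineligible. They are shared with cancellations (never treated, 13.9), major violations (not removed by 16.324) and replacements. The treated-ineligible share is not stated.

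**2. Which patients count where.**

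| Patient | 16.52 stopping rule | 16.324 rates |
|---|---|---|
| Eligible, treated at the final dose level | counted | counted |
| Treated at the final dose level, later ruled ineligible | counted | not counted |
| Eligible, treated at an abandoned dose level | not counted | counted |
| Treated at an abandoned dose level, later ruled ineligible | not counted | not counted |

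The second row is the point at issue. The third shows that the sets can also differ by dose level if the starting dose is reduced.

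**3. Effect on a rate.** Let N be the eligible treated patients, x those with the event, k the treated-ineligible patients and j those of them with the event. The plan reports x/N; the rate in all exposed patients is (x + j)/(N + k). The difference is

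(x + j)/(N + k) − x/N = (jN − kx) / [N(N + k)],

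which is zero when j/k = x/N, that is, when ineligible patients have the same event rate as eligible ones.

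**4. Illustration.** All counts are assumed: N = 56 (the evaluable target, used here for eligible treated patients), x = 6, k = 3. The plan reports 6/56 = 10.7% (exact 95% CI 4.0 to 21.9%).

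| Events among the 3 ineligible | All treated | Difference in percentage points |
|---|---|---|
| 0 | 6/59 = 10.2% | (0 − 18)/3304 = −0.5 |
| 1 | 7/59 = 11.9% | (56 − 18)/3304 = +1.2 |
| 2 | 8/59 = 13.6% | (112 − 18)/3304 = +2.8 |
| 3 | 9/59 = 15.3% (CI 7.2 to 27.0%) | (168 − 18)/3304 = +4.5 |

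**5. Range.** The next figures are ceilings: N = 56, and every treated-ineligible patient has the event.

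| k (assumed) | x = 0; plan reports 0/56 = 0% (CI 0 to 6.4%) | x = 3; plan reports 3/56 = 5.4% |
|---|---|---|
| 1 | 1/57 = 1.8% | 4/57 = 7.0% |
| 3 | 3/59 = 5.1% | 6/59 = 10.2% |
| 5 | 5/61 = 8.2% | 8/61 = 13.1% |
| 7 (whole allowance) | 7/63 = 11.1% | 10/63 = 15.9% |

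For one to five such patients, the filter lowers a rate by at most about 2 to 8 points. At the other extreme, with x = 3, k = 5 and no events among the ineligible, the all-treated rate is 3/61 = 4.9%, slightly below the reported 5.4%.

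**The case against.** The strongest reply is that the effect is small and the mechanism unproven. Much of that stands.

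- **Inference.** A reader might infer that a toxicity triggers its own removal. No text says that eligibility rulings follow toxicity, and 13.7 asks about status at registration. Eligibility is verified at registration (6.32). Pulmonary function tests and PET-CT are required at baseline (4.0), and motor neuropathy, pneumonitis and dyspnea are graded then (10.54). Late discovery is possible but made less likely.
- **Pancreatitis.** It is tempting to add this to the overlapping exclusions. Section 3.29g requires a known history, so a history first found during work-up of an event may not make the patient ineligible. It is not a sound example.
- **Data collection.** A reader might infer that 13.7 lets data lapse once ineligibility is confirmed. The documents do not support that. Section 13.7 also requires event monitoring under Section 18.0, which is not in the text available here, so what it collects cannot be judged. Serious events (10.41, 10.53) and deaths (10.331, 10.5531) are reportable without regard to eligibility.
- **Patient protection.** The stopping rule and the monitoring board's safety review (16.51) carry no eligibility filter. The adverse event tables are descriptive and test no hypothesis, and the efficacy decision is untouched.
- **Magnitude.** The 4.5-point gap needs all three assumed ineligible patients to have the event, against 10.7% of the others.

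These points limit the size and reach of the problem. None is a reason to filter a safety set by eligibility.

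**Conclusion.** The concern holds for the reported rates in 16.324 and for nothing beyond them. Following the plan as written, a treated patient later ruled ineligible counts in 16.52 but not in the published toxicity.

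The direction of any bias rests on an inference: that conditions which overlap with the toxicities make both an event and an ineligibility ruling more likely. The size rests on assumed counts: 10.7% against 15.3% at the extreme of the illustration, and close to no change if ineligibility is unrelated to toxicity. The effect would be most visible for rare serious events, where one or two patients decide whether a rate is reported as zero. It would be wrong to conclude that the trial's toxicity will be materially understated or that safety oversight is weakened; the documents show neither. This is a modest defect in the definition of the analysis set, and nearly free to correct.

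**What to change.** Replace the denominator sentence in 16.324 with: *All patients who receive at least one dose of either study drug, regardless of eligibility, are evaluable for adverse events, summarised by starting dose level.*

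The dose-level clause is needed because 16.52 covers only the final dose level. With it, the final-dose-level table uses the same population as the stopping rule even if the starting dose is reduced. Keep eligible-only rates as a supplementary table. No change to 13.7 is proposed.

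The cost is one sentence and one extra table. Sample size, decision rules and treatment do not change. The downside is that the reported toxicity rates may look slightly less favourable.

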2.2 Secondary

2.21 The complete metabolic response (CMR) rate

2.22 Safety and tolerability of the regimen in this patient population

2.23 Duration of response (DOR)

2.24 Progression-free survival (PFS)

2.25 Overall survival (OS)

2.3 Correlative Research

2.31 T-cell/cytokine– peripheral blood specimens will be used to assess T-cell activation and cytokine up regulation as measures of treatment effect. This goal will be exploratory in nature and reported descriptively.

2.32 Biomarkers- intratumoral cell populations, genetic variability, serum cytokines and T-cell activation will be evaluated to identify potential biomarkers that correlate with response to therapy. This goal will also be exploratory in nature.

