3.1 Registration – Inclusion Criteria

3.11 Classical Hodgkin Lymphoma determined by local hematopathology review

3.12 One of the following:

- Age \geq 60 years
- Age <60 years but unsuitable for standard chemotherapy because of a cardiac ejection fraction of <50%, a pulmonary diffusion capacity <80%, or a creatinine clearance \geq 30 and <60 mL/min, or refused standard chemotherapy despite efforts to convince them otherwise.

Cockcroft-Gault Equation:

$$\text{Creatinine clearance for males} = \frac{(140 - \text{age})(\text{weight in kg})}{(72)(\text{serum creatinine in mg/dL})}$$

$$\text{Creatinine clearance for females} = \frac{(140 - \text{age})(\text{weight in kg})(0.85)}{(72)(\text{serum creatinine in mg/dL})}$$

- 3.13 Requirement for systemic chemotherapy: all stages except IA (not bulky disease), if involved field is considered Radiotherapy (RT) curative.
- 3.14 Previously untreated with either chemotherapy, radiation therapy or either brentuximab vedotin or nivolumab, or another check point inhibitor.
- 3.15 ECOG Performance Status (PS) 0, 1, or 2 (Appendix II)
- 3.16 The following laboratory values obtained ≤ 7 days prior to registration.
- Absolute neutrophil count (ANC) $\geq 1500/\text{mm}^3$, unless secondary to bone marrow involvement.
 - Leukocytes $\geq 3,000/\text{mm}^3$
 - Platelet count $\geq 100,000/\text{mm}^3$
 - Hemoglobin >9.0 g/dL – unless determined by treating physician to be disease related
 - Total bilirubin ≤ 1.5 x upper limit of normal (ULN)
 - Aspartate transaminase (AST) ≤ 2.5 x ULN
 - Alanine Transaminase (ALT) ≤ 2.5 x ULN
 - Creatinine ≤ 2.0 mg/dL
 - Amylase and/or lipase ≤ 1.5 x ULN
- 3.17 Women of childbearing potential must have a negative serum or urine pregnancy test (minimum sensitivity 25 IU/L or equivalent units of HCG) within 24 hours prior to registration

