6.3 Safety Analysis Cohort and Phase II Cohort

6.31 Correlative Research

A mandatory correlative research component is part of this study. The patient will be automatically registered onto this component (see Sections 3.0, 14.0 and 17.0).

6.32 Prior to accepting the registration, registration/randomization application will verify the following:

- IRB approval at the registering institution
- Patient eligibility
- Existence of a signed consent form
- Existence of a signed authorization for use and disclosure of protected health information

6.33 Documentation of IRB approval must be on file in the Registration Office before an investigator may register any patients. Approvals should be uploaded using the online ACCRU Regulatory Management System (ARMS).

In addition to submitting initial IRB approval documents, ongoing IRB approval documentation must be on file (no less than annually) with ACCRU. Approvals should be uploaded using online ACCRU Regulatory Management Systems (ARMS). If the necessary documentation is not submitted in advance of attempting patient registration, the registration will not be accepted and the patient may not be enrolled in the protocol until the situation is resolved.

Submission of annual IRB approvals is required until the study has been closed through your IRB.

- 6.34 At the time of registration, the following will be recorded:
- Patient has/has not given permission to store and use his/her sample(s) for future research to learn about, prevent, or treat cancer.
 - Patient has/has not given permission to store and use his/her sample(s) for future research to learn, prevent, or treat other health problems (for example: diabetes, Alzheimer's disease, or heart disease).
 - Patient has/has not given permission for ACCRU to give his/her sample(s) to outside researchers.
- 6.35 Treatment on this protocol must commence at an ACCRU institution under the supervision of a medical oncologist or hematologist.
- 6.36 Treatment cannot begin prior to registration and must begin ≤ 14 days after registration.
- 6.37 Pretreatment tests/procedures (see Section 4.0) must be completed within the guidelines specified on the test schedule.
- 6.38 All required baseline symptoms (see Section 10.54) must be documented and graded.
- 6.39a Study drug is available on site.
- 6.39b Blood draw kit is available on site. Kits must be used for this study.

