10.54 Baseline and Adverse Events Evaluations

Pre-treatment symptoms/conditions to be graded at baseline and adverse events to be graded at each evaluation per the CTCAE v4.0 grading unless otherwise stated in the table below:

System Organ Class	Adverse event/Symptoms	Baseline	Each evaluation
Nervous System Disorders	Peripheral motor neuropathy	X	X
Investigations	Creatinine increased	X	X
Respiratory, thoracic and mediastinal disorders	Pneumonitis	X	X
	Dyspnea	X	X

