10.55 Case Report Forms - Academic and Community Cancer Research United (ACCRU)

Submit the following AEs not specified in Section 10.5 (paper or electronic, as applicable)

10.551 Grade 2 AEs deemed *possibly, probably, or definitely* related to the study treatment or procedure.

10.552 Grade 3 and 4 AEs regardless of attribution to the study treatment or procedure.

10.553 Grade 5 AEs (Deaths)

10.5531 Any death within 100 days of the patient's last study treatment or procedure regardless of attribution to the study treatment or procedure.

10.5532 Any death more than 100 days after the patient's last study treatment or procedure that is felt to be at least possibly treatment related must also be submitted as a Grade 5 AE, with a CTCAE type and attribution assigned.

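### The adverse event tables use each patient's maximum grade and ignore the required baseline grades, so low-grade rates of the solicited terms may include stable pre-existing findings

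*Combined protocol and SAP*

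**What the plan says.** Goal 2.22 is "Safety and tolerability of the regimen in this patient population". Section 16.324 serves it with this rule: "The maximum grade for each type of adverse event will be recorded for each patient, and frequency tables will be reviewed to determine patterns". The next sentence adds: "Additionally, the relationship of the adverse event(s) to the study treatment will be taken into consideration". The section defines no treatment-emergent event, sets no new-or-worsened condition and does not mention a baseline grade.

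The baseline grades are nevertheless collected. Section 10.54 reads "Pre-treatment symptoms/conditions to be graded at baseline and adverse events to be graded at each evaluation per the CTCAE v4.0 grading", and its table lists peripheral motor neuropathy, creatinine increased, pneumonitis and dyspnea, each marked for baseline and for each evaluation. Section 6.38 makes this a condition of registration: "All required baseline symptoms (see Section 10.54) must be documented and graded".

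Section 10.55 sets the reporting filters for other events under the lead-in "Submit the following AEs not specified in Section 10.5". Grade 2 events are submitted only if at least possibly related, and Grade 3 and 4 events whatever their attribution. Grade 1 events are not on the list.

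**The concern.** A maximum grade measures toxicity only if the patient started at zero or if the starting grade is taken into account. This trial enrols patients aged 60 or older. It also enrols younger patients who may qualify as "unsuitable for standard chemotherapy because of a cardiac ejection fraction of <50%, a pulmonary diffusion capacity <80%, or a creatinine clearance" in the range given in Section 3.12. Some of them can be expected to carry a grade above zero on a solicited term before the first dose. If that grade persists unchanged, it is the patient's maximum and looks the same in the table as an event that began on treatment.

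The descriptive safety profile is at stake: any-grade and Grade 1-2 rates for dyspnea, creatinine and motor neuropathy. The protocol uses baseline values elsewhere. Several dose-modification entries in Section 8.2 refer to return to the baseline grade, and Section 16.331 analyses biomarkers by baseline value and change. The safety analysis does neither, so the counting rule is left open until the data have been seen.

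**Working it through.** Section 16.324 states no figure, so there is none to reproduce. The check is a reading of the rules, followed by an illustration of scale.

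**1. Which terms are exposed.** The 10.55 filters apply to events not already specified in Section 10.5, most naturally the 10.54 list. The four listed terms are therefore graded at every evaluation at any grade and whatever the attribution. Taking each in turn:
- Dyspnea: no eligibility criterion limits it by grade.
- Creatinine increased: Section 3.16 admits values up to 2.0 mg/dL. Take an assumed 50-year-old man of 80 kg. By the protocol's Cockcroft-Gault formula, a clearance of 60 mL/min corresponds to (140 − 50) × 80 / (72 × 60) = 1.67 mg/dL, so he enters by the renal route with creatinine above 1.67 and up to 2.0. The CTCAE grade depends on cut-offs that the documents do not reproduce.
- Peripheral motor neuropathy: Section 3.29d excludes Grade 2 or higher neuropathy, so the baseline grade is at most 1.
- Pneumonitis: Section 3.25 excludes a history of interstitial lung disease, so a baseline grade should be rare.

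**2. What the rule does with four constructed patients.**

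| Patient | Term | Baseline grade | Worst grade on study | Entry under 16.324 | New or worse? |
|---|---|---|---|---|---|
| A | Dyspnea | 2 | 2 | Grade 2 | No |
| B | Motor neuropathy | 1 | 1 | Grade 1 | No |
| C | Dyspnea | 0 | 2 | Grade 2 | Yes |
| D | Dyspnea | 1 | 2 | Grade 2 | Yes |

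In an all-cause table A, C and D are identical. Only the baseline column separates them.

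**3. Scale.** Let b be the share of patients with a baseline grade of 1 or more on a term, and r the share with a new or worsened event, taken as the same with and without a baseline grade. The documents give neither, so both are assumptions. If every stable case is tabulated:

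tabulated any-grade rate = b + (1 − b) × r

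patients counted with no change, scaled to the 56 evaluable patients of Section 16.22 = 56 × b × (1 − r)

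With r = 15%:

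| b | Tabulated rate | Ratio to 15% | Unchanged patients counted |
|---|---|---|---|
| 10% | 0.10 + 0.90 × 0.15 = 23.5% | 1.57 | 56 × 0.10 × 0.85 = 4.8 |
| 20% | 0.20 + 0.80 × 0.15 = 32.0% | 2.13 | 56 × 0.20 × 0.85 = 9.5 |
| 30% | 0.30 + 0.70 × 0.15 = 40.5% | 2.70 | 56 × 0.30 × 0.85 = 14.3 |

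Over a wider grid (b from 5% to 30%, r from 5% to 20%) the tabulated rate runs from 0.05 + 0.95 × 0.05 = 9.8% to 0.30 + 0.70 × 0.20 = 44%. With b = 0, or if attribution removes every stable case, there is no overstatement. These figures are the upper end of the possible effect.

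**4. Trial decisions.** The DLT definition (7.12) and the adverse event stopping rule (16.52) both require Grade 4 or higher and at least possible relatedness. A stable low baseline grade meets neither rule.

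**The case against.** The strongest reply is that the plan never says a stable condition counts as an adverse event. Section 10.54 words pre-treatment conditions separately from adverse events, and Section 10.0 ties an adverse event to use of a drug. Investigators also hold the baseline grade when they assign attribution, and Section 10.3 offers unlikely and unrelated categories. This stands in part. A reader might infer that the plan deliberately counts pre-existing conditions as toxicity; the documents do not support that, because they are silent. Attribution does not settle the matter, however: 16.324 gives no rule for applying it, and an all-cause table ignores it.

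Other stronger readings also go too far:
- **Neuropathy in general.** Section 10.54 lists only motor neuropathy. Sensory neuropathy falls under 10.55, where Grade 1 is not submitted and Grade 2 only if at least possibly related, and no baseline sensory grade is mandated. It is outside this point.
- **Dyspnea from low ejection fraction.** Section 3.27 lists symptomatic congestive heart failure among its exclusions. The 3.12 impairment criteria are organ-function thresholds, not symptoms, and apply only under age 60.
- **Comparison with all cited background rates is invalid.** The toxicity rates for older patients in Section 1.1 are mainly for higher grades, which are little affected. The mismatch is with the treatment-emergent rates in 1.225 and 1.229b. The overlap with the exposed terms is limited there too, chiefly peripheral neuropathy reported as a group.
- **Decisions are distorted.** No formal rule is touched, although 16.25 and 16.52 allow the wider adverse event picture to inform judgement.

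It can also be said that unadjusted worst-grade tables err on the cautious side. That is a good reason to keep them, but not to leave out the baseline comparison.

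**Conclusion.** The point holds in limited form. Following 16.324 as written gives an all-cause table that cannot distinguish a stable pre-existing grade from a new or worsened event for dyspnea, creatinine increased and Grade 1 motor neuropathy. Low-grade rates for these terms may be overstated and are not like-for-like with treatment-emergent rates.

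The documents do not allow the size to be fixed. The tripling that the highest row of the illustration approaches (a factor of 2.70) should not be read as an estimate. It assumes that 30% of patients have a baseline grade, that 15% have a new or worsened event, and that every stable case is tabulated whatever its attribution. The consequence is confined to the descriptive safety output for goal 2.22. This is a free or cheap improvement, not a flaw in the trial's decision rules.

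**What to change.** Keep the all-cause maximum-grade table. Add to Section 16.324, before safety data are tabulated, wording such as:

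*For each term listed in Section 10.54, baseline grade will be cross-tabulated against the worst grade after first dose. The number and percentage of patients whose worst grade after first dose exceeds their baseline grade will be reported, for all events and for events at least possibly related to treatment. A term absent at baseline is assigned baseline grade 0.*

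The cost is a short addition to the text and one extra table. The data are already mandatory under 6.38 and 10.54, so no visit, form or assessment is added. There is one small downside: an event that resolves and then recurs at its baseline grade is not counted as new. It remains visible in the unadjusted table, which is why both should be shown.
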